at the start of the study and for up to 1 year after the study is completed, if there are changes that affect my financial disclosure status.

I agree to ensure that the confidential information contained in this document will not be used for any purpose other than the evaluation or conduct of the clinical investigation without the prior written consent of Amgen Inc.

Signature

Name of Principal <<or Coordinating>> Investigator Date (DD Month YYYY)

Title: An International, Randomized, Double-blind, Placebo-controlled, Phase 2 Study of AMG 479 with Exemestane or Fulvestrant in Postmenopausal Women with Hormone Receptor Positive Locally Advanced or Metastatic Breast Cancer

Study Phase: 2

Indication: Postmenopausal women with hormone receptor (HR)-positive, locally advanced or metastatic breast cancer who have disease progression during or within 12 months after completing prior adjuvant endocrine therapy or during the first prior endocrine therapy for metastatic disease

Primary Objective: To provide an estimate of the relative efficacy of Arm A (AMG 479 in combination with endocrine therapy [exemestane or fulvestrant] versus Arm B (AMG 479 placebo in combination with endocrine therapy [exemestane or fulvestrant]) as measured by the progression free survival (PFS) hazard ratio. This estimate will be precise enough to provide guidance for further development of AMG 479.for use in the planning of a phase 3 study in this patient population. Additionally, this study will provide qualitative estimates of PFS for treatment arms A and B.

Secondary Objectives: To investigate the effect of AMG 479 compared with placebo when administered in combination with exemestane or fulvestrant on:

- the safety and tolerability
- the impact to patient reported outcomes (PROs)
- the pharmacokinetics (PK) of AMG 479
- additional efficacy measures including clinical benefit rate, objective response rate, duration of response, time to progression (TTP), time-to-response, time-to-treatment failure, and survival time

Exploratory Objectives: To assess the potential effect of co-administration of AMG 479 and endocrine therapy (exemestane or fulvestrant) on the PK of the endocrine therapy (exemestane or fulvestrant).

To investigate the effect of AMG 479 compared with placebo when administered in combination with exemestane or fulvestrant on biomarkers using biochemical analysis of blood and tumor samples, including the correlation between biomarker measurements at baseline and/or in response to treatment outcomes.

To investigate the effect of genetic variation in drug metabolism genes, breast cancer genes, and drug target genes on treatment outcomes (this part of the study is optional for subjects).

Hypothesis: This study will provide an estimate of the relative efficacy of AMG 479 in combination with endocrine therapy (exemestane or fulvestrant) versus AMG 479 placebo in combination with endocrine therapy (exemestane or fulvestrant) as measured by the PFS hazard ratio. Additionally, this study will provide the estimate of PFS for each treatment arm.

Study Design: This is a randomized, double-blind, placebo-controlled, phase 2 study. Subjects will include postmenopausal women with confirmed hormone receptor (HR)-positive, locally advanced or metastatic breast cancer, who have disease progression during or within 12 months after completing prior adjuvant endocrine therapy or during the first prior endocrine therapy for metastatic disease.

Based on investigator discretion, subjects will be prescribed an endocrine therapy of either exemestane or fulvestrant to be administered throughout the study. The study plans to randomize 150 subjects in a 2:1 ratio to Arm A: AMG 479 in combination with endocrine therapy (exemestane or fulvestrant) or Arm B: placebo in combination with endocrine therapy (exemestane or fulvestrant).

At least 45 of the 150 subjects randomized will be required to be prescribed to each endocrine therapy (exemestane and fulvestrant).

Study treatment with AMG 479 or placebo and endocrine therapy (exemestane or fulvestrant) will continue until disease progression, unacceptable toxicity, consent withdrawal, investigator discretion, initiation of a new anticancer treatment, or death.

Subjects randomized to placebo in combination with endocrine therapy (Arm B) may have the opportunity to continue receiving study treatment as open-label AMG 479 in combination with the endocrine therapy originally prescribed ('roll over treatment') upon disease progression.

In order to safeguard the interest of the study subjects and maintain the study integrity, Amgen will form an unblinded data review team (DRT) that is external to the study team involved in the daily conduct of the study, but internal to Amgen to review safety data and efficacy analysis results.

Endpoints:

Primary: Progression free survival (PFS), as measured by Response Evaluation Criteria in Solid Tumors criteria (modified RECIST) per local review

Secondary:

- Clinical benefit (complete response, or partial response, or stable disease for ≥ 24 weeks as measured by modified RECIST per local review), objective response rate (complete and partial response as measured by modified RECIST per local review), duration of response, TTP, time-to-response, time-to-treatment failure, and survival
- Incidence of adverse events, abnormal laboratory values, and anti-AMG 479 antibody formation
- PK parameters of AMG 479
- Breast cancer related symptoms, health related quality of life, and skin toxicity burden

Exploratory: Objective response by tumor mutation status, biochemical concentrations and abundance of drug targets in tumor tissue and blood samples, genetic variations in drug metabolism genes and target genes (optional, separate informed consent required).

Sample Size: The study plans to randomize 150 subjects in a 2:1 ratio to Arm A: AMG 479 in combination with endocrine therapy (exemestane or fulvestrant) or Arm B: placebo in combination with endocrine therapy (exemestane or fulvestrant).

Key Subject Eligibility Criteria:

Inclusion

- Histologically or cytologically confirmed carcinoma of the breast with locally advanced or metastatic disease not amenable to surgery or radiation with curative intent (based on medical history review)
- Confirmation of HR (estrogen and/or progesterone receptor) positive disease using institutional standards for analysis of the primary tumor tissue or tissue obtained thereafter (based on medical history review)
- Amenable to receive endocrine therapy as per investigator discretion
- Disease progression while receiving prior endocrine therapy for locally advanced or metastatic breast cancer or recurrence while receiving prior endocrine therapy as adjuvant treatment or within 12 months of treatment discontinuation.
- Measurable or non-measurable disease, as defined by the modified RECIST criteria
- Eastern Cooperative Oncology Group performance status of 0 or 1
- Postmenopausal woman (as defined by the protocol) \geq 18 years old

- Adequate renal and hepatic function
- Adequate glycemic function, for subjects with known diabetes (Type 1 or 2)

Exclusion

- HR-unknown, or -negative disease (based on medical history review)
- Not amenable to receive endocrine therapy, including but not limited to, inflammatory breast cancer, rapidly progressing disease, or symptomatic visceral disease
- Central nervous system metastases, unless previously treated by either radiation therapy and/or surgical resection, who are clinically stable off corticosteroids before randomization
- More than 1 prior endocrine regimen for metastatic breast cancer, or locally advanced breast cancer. There are no restrictions for their administration in the neoadjuvant or adjuvant settings, except subjects should not have previously been treated with the endocrine therapy planned for use in this study
- More than 1 prior regimen including immunotherapy (eg, vaccines), antibody therapy (eg, trastuzumab, bevacizumab), small-molecule therapy (eg, lapatinib) for metastatic breast cancer, or locally advanced breast cancer, although there are no restrictions for their administration in the neoadjuvant or adjuvant settings
- More than 1 prior regimen including chemotherapy for metastatic breast cancer, or locally advanced breast cancer, although there are no restrictions for their administration in the neoadjuvant or adjuvant settings
- Administration of prior endocrine anticancer therapies within 1 week of randomization
- Administration of other prior anticancer therapies within 2 weeks of randomization

Key Subject Inclusion Criteria for Roll Over Treatment:

- Plan to continue study treatment as roll over treatment with open-label AMG 479 and the endocrine therapy prescribed at screening, if deemed to have been randomized to Arm B (placebo in combination with endocrine therapy [either exemestane or fulvestrant])
- Disease progression (according to local review using modified RECIST criteria) while receiving blinded study treatment
- Able to receive first dose of open-label AMG 479 within 4 weeks of disease progression
- Amenable to continue receiving endocrine therapy prescribed at screening, as per investigator discretion
- ECOG performance status of 0 or 1
- Adequate renal and hepatic function
- Adequate glycemic function, for subjects with known diabetes (Type 1 or 2)

Study Treatment Dosage and Administration: The AMG 479 dose to be used in the study is 12 mg/kg IV every 2 weeks. Based on investigator discretion, subjects will be prescribed an endocrine therapy of either exemestane (25 mg tablets once a day [QD] by mouth [PO]) or fulvestrant (loading dose [500 mg intramuscular (IM) on study day 1, then 250 mg IM on study day 15] then 250 mg IM on study day 29 and every 28 days thereafter) to be administered throughout the study. **AMG 479 or placebo will be administered by IV infusion through a peripheral line or indwelling catheter using a nonpyrogenic, low protein binding filter with a 0.2- or 0.22-micron pore size in-line filter infusion set-up.**

Procedures: Informed consent, radiological assessments including bone scan and CT or MRI scans, clinical evaluations, hematology, coagulation factors, chemistry, HgbA1c, urine analysis, AMG 479, PK, biomarker and tumor tissue collection, concomitant medication collection, adverse event collection, and completion of PRO questionnaires.

Statistical Considerations: The sample size of 150 subjects randomized in a 2:1 ratio for test versus control (Test: AMG 479 + fulvestrant or exemestane; Control: placebo + fulvestrant or exemestane) is intended to generate treatment effect estimates that may aid in the design of a potential phase 3 program for AMG 479. The desired increase in the median PFS, for subjects that received AMG 479 in combination with endocrine therapy that is believed to be clinically meaningful is 2 months (with a minimum increase of 1.5 months). Using a median PFS of 4 months for the treatment of placebo in combination with endocrine therapy (exemestane or fulvestrant), a 2 month absolute increase (50% relative increase) in the median PFS translates into a hazard ratio of 0.667 [test(n = 100)/control(n = 50)] and a 1.5 month absolute increase (37.5% relative increase) in the median PFS translates into a hazard ratio of 0.727.

Interim analyses of safety data will occur at the time 12 and 30 subjects have completed treatment administration for 2 months to assess safety and tolerability of the combination of AMG 479 or placebo with endocrine therapy (exemestane or fulvestrant). The DRT, will review cumulative safety data and make recommendations regarding study conduct. An interim analysis of efficacy and safety data is planned at the time 75 PFS events have occurred. This is estimated to occur approximately one month after the last subject is randomized. Summary statistics and Kaplan-Meier (K-M) plots of PFS by treatment arm, 80% confidence intervals for the estimated hazard ratio and the K-M estimated proportion of subjects without a PFS event at 6 months post-randomization will be generated. The stratified Cox model will be used to estimate the hazard ratio with respect to PFS (using the stratification factors) and to produce an 80% confidence interval for the hazard ratio.

All primary and secondary efficacy analyses will be conducted on the full analysis set. Subjects will be included in the analysis according to their randomized treatment assignment. The primary efficacy analysis will be performed when approximately 120 PFS events have been observed, where progression is based on local review. This is estimated to occur approximately 23 months after the first subject is randomized. At the time of the primary efficacy analysis, summaries will be provided for each safety, efficacy and PRO endpoint. The primary analysis of PFS will use the same methods utilized for the interim analysis of PFS.

Sponsor/Licensee: Amgen Inc.

Product: AMG 479 Protocol Number: 20060362 Date: Amendment 2, 01 June 2011

	Screen	study Treatment																	Safety FU°	Long-term FU ^p			
Cycle			1		2 2			3		4	5			6	7		8			Assess for			
Cycle		•			2		5		•	5			Ū		'		5		Roll Over ⁿ	ΗI			
Cycle Days	-28	1	2	15	1	15	1	15	1	15	1	15	1	15	1	15	1	15			DE/		
Study Week	-4		1	3	5	7	9	11	13	15	17	19	21	23	25	27	29	31	H		OR		
ENDOCRINE TREATMENT ADMINISTRATION ^a																			DE/		NO		
Exemestane		ł																\rightarrow	R	Х	ЗET		
Fulvestrant		Х		Х	Х		Х		Х		Х		Х		Х		Q4W		NO	Х	ISCF		
INVESTIGATIONAL PRODUCT ADMINISTRATIO	N																		RET		PID		
AMG 479 or Placebo		Х		Х	Х	Х	Х	Х	Х	Х	Х	Х	Х	Х	Х	Х	Х	Q2W	SC		۲Ľ,		
GENERAL AND SAFETY ASSESSMENTS																			PID		RAV		
Informed Consent	Х																		Å,		문		
Review of Eligibility	Х																		RA	х	.M.		
Medical History/Clinical Evaluation ^b	х	Х			х		X		х		х		x		х		Q4W		문	х	ENT	х	
Weight and Height ^c	Х	Х		Х	Х	Х	Х	Х	Х	Х	Х	Х	Х	Х	Х	Х	Х	Q2W	N	Х	SNC	Х	
Vitals ^d	Х	Х		Х	Х	Х	Х	Х	Х	Х	Х	Х	Х	Х	Х	Х	Х	Q2W	EN	Х	č,	Х	
12-Lead ECG	Х																		SNC		CI		
Prior and Current Medication Collection	←																		Š	Х	XO.	Х	
Adverse Events Collection	Ļ																	\rightarrow	ICT	Х	Ē	Х	
LABORATORY ASSESSMENTS																			õ		LAB		
Blood Chemistry ^e	Х	Xg		Х	Х	Х	Х	Х	Х	Х	Х		Х		Х		Q4W		Ë	Х	EP	Х	
Hematology	Х	Х	Х	Х	Х	Х	Х	Х	Х	Х	Х	Х	Х	Х	Х	Х	Х	Q2W	TAB	X	ACC	Х	
Creatinine/Calculated Creatinine Clearance ^f	х																		Ē	Х	, UN		
Coagulation	х	Xg			Х				х				х				Q8W		AC	Х	Od .	х	
тѕн	х	Xg			х				х				х				Q8W		S	Х	ENT	Х	
HgbA1C		Xa			Х				х				х				Q8W		8	х	В	Х	
Endocrine Biomarker Collection		Х		х	Х		х				Х				Q8W				IL	х	BSI	Х	
Other Biomarker Collection		Х		Х			Х				Х				Q8W				ns.	Х		Х	
Pharmacokinetics ^h		Х		Х	Х		Х				Х				Q8W				EN	х	IL	Х	
Anti-AMG 479 Antibody Assay		Х			Q24W	1													SSM	Х	LS U	Х	
TUMOR RELATED ASSESSMENTS																			SE		EN		
Radiological Assessement ⁱ	Х	1		1	1		X	1	1		Х	1	1	1	Q8W		1		EA		SSM		Х
Bone Scan ^j	Х								х								Q12W		N		SSE		х
Tumor Marker CA 15-3 or CA 27-29 ^k	x						x				х				Q8W				ONT		IE A:		
Tumor Sample ^l	x																		o		INU		
PRO Assessments ^m	1	х	İ		x		x		x					l	Q12W		1			х	NO	х	
Survival Status	1																				0		X

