Appendix A. Schedule of Assessments

- a Endocrine therapy (exemestane or fulvestrant) will be prescribed based on investigator discretion. Patients prescribed exemestane will have compliance reviewed and discussed with subject if needed at every clinic visit.
- b Clinical evaluation, including physical exam performed, and ECOG status
- c Height will only be collected at screening. Weight will be required pre-infusion to access the IVRS to obtain box assignment, quantity of vials and the volume of AMG 479 or placebo for infusion.
- d Vitals, include blood pressure and respiration rate, pulse, and temperature.
- e Blood chemistry will be analyzed at the local laboratory and will include: sodium, potassium, chloride, creatinine, CO₂, BUN, AST, ALT, alkaline phosphatase, and total bilirubin. Additionally fasting/non-fasting glucose will be assessed (fasting: screening, day 1 of cycles 1-4 then every second cycle, roll over treatment assessment [if applicable], and safety follow-up; non-fasting: day 15 of cycles 1-4, and day 1 cycle 5, then every second cycle)
- f Either serum creatinine or calculated creatinine clearance (by Crockcroft-Gault formula)
- g These laboratory assessments do not need to be performed on cycle 1 day 1 if they were performed during screening within 7 days of initiation of treatment
- h Blood collections for PK analysis will occur for AMG 479 (pre- and post-AMG 479 infusion thru cycle 3), for exemestane (only for subjects prescribed exemestane; pre- and post-exemestane administration thru cycle 3), and for fulvestrant (only for subjects prescribed fulvestrant; pre-fulvestrant IM injection only thru cycle 3). No PK sample collection is needed for post-fulvestrant IM injection. Thereafter, blood collection for PK analysis of AMG 479, exemestane, and fulvestrant will only occur pre-dose every 2 cycles, starting cycle 5.
- i Radiological assessments of the chest, abdomen and pelvis may occur by CT or MRI. The same technique used in screening must be used throughout the study. CT or MRI radiological assessments should occur on day 1 of cycle 3, then every 7 to 8 weeks thereafter.

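### Does triggering the two safety looks on subjects who complete 2 months of treatment let early toxicity delay the safety review?

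*Combined protocol and SAP*

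**What the plan says.** The Synopsis, Statistical Considerations, sets the two looks by a count of subjects: "Interim analyses of safety data will occur at the time 12 and 30 subjects have completed treatment administration for 2 months". The stated aim is to assess safety and tolerability of the combination. On what is reviewed, it says: "The DRT, will review cumulative safety data and make recommendations regarding study conduct".

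The Synopsis, Study Design, says that study treatment "will continue until disease progression, unacceptable toxicity, consent withdrawal", and then lists further reasons for ending it. The same section sets up the DRT as an unblinded group outside the study team that reviews safety data and efficacy results. It does not confine the safety review to the two looks.

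The next planned analysis covers efficacy and safety at 75 PFS events. Of its timing the Synopsis says: "This is estimated to occur approximately one month after the last subject is randomized". Appendix A schedules adverse event collection through treatment and follow-up.

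The text available for this review is the Synopsis and Appendix A. The body of the protocol may define the trigger more fully.

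**The concern.** The trigger sentence has no clause for subjects who discontinue earlier, and no calendar or enrolment backstop. Unacceptable toxicity is one of the listed reasons for ending treatment. A subject who stops for toxicity at week 5 has not completed 2 months, so another subject must reach 2 months in her place. The dependence therefore runs the wrong way: the worse the early tolerability of AMG 479, the later the review meant to detect it.

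The 75-event analysis is expected only after enrolment has closed. In the text at hand, these two looks are thus the scheduled safety reviews that fall during enrolment. If the delay were long, or if early stoppers were left out of the data reviewed, subjects could go on being randomized while a safety signal waited.

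**Working it through.** **Inputs from the Synopsis.** Triggers k = 12 and 30; 150 subjects, 2:1 (100 and 50); "Using a median PFS of 4 months for the treatment of placebo in combination with endocrine therapy", and a 2-month increase to 6 months on AMG 479. The hazard ratios reproduce: 4/6 = 0.667 and 4/5.5 = 0.727. The triggers are chosen counts without a stated derivation, so there is nothing to reproduce for them.

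**Inputs not in the documents.** The share d of AMG 479 subjects who stop for toxicity before 2 months, and the accrual rate r. For d, 10%, 20% and 30% are assumed.

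**Step 1: subjects needed.** The share of all subjects who complete 2 months is f = 1 − (2/3)d, so on average k/f must be randomized to obtain k completers.

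| d | f | 12/f | 30/f |
|---|---|---|---|
| 10% | 0.933 | 12.9 | 32.1 |
| 20% | 0.867 | 13.8 | 34.6 |
| 30% | 0.800 | 15.0 | 37.5 |

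The excess k/f − k is at most 3 and 7.5 subjects. It is also the expected number of early toxicity stoppers among those k/f subjects, and the DRT has their data at the look.

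**Step 2: accrual.** The two stated timings limit r = 150/A, where A is the accrual period in months. The Synopsis places the 75-event analysis about one month after the last randomization, and says of the analysis at about 120 events: "This is estimated to occur approximately 23 months after the first subject is randomized". With uniform entry over A, hazard λ = ln 2/median and censoring hazard c per month, a subject followed for u months has had an event with probability λ/(λ+c) × (1 − exp(−(λ+c)u)). Setting the expected events at A + 1 to 75 gives:

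| Progression observed | c | A | r | Events at month 23 |
|---|---|---|---|---|
| continuously | 0 | 9.4 | 15.9 | 135.0 |
| continuously | 0.01 | 10.0 | 15.0 | 127.1 |
| continuously | 0.02 | 10.6 | 14.1 | 119.9 |
| continuously | 0.03 | 11.4 | 13.1 | 113.3 |
| at 8-week scans | 0.01 | 12.8 | 11.7 | 120.4 |

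The third and fifth rows both fit the two timings, so the documents do not settle the accrual rate. As a slow extreme, A = 18 (r = 8.3, no censoring) gives 120 events at month 23, but 99.6 rather than 75 one month after accrual ends.

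**Step 3: delay.** The delay is (k/f − k)/r months, here for look 1 / look 2, with days at 30.4 per month in brackets.

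| d | r = 14.1 | r = 11.7 | r = 8.3 (extreme) |
|---|---|---|---|
| 10% | 0.06 / 0.15 (2 / 5) | 0.07 / 0.18 (2 / 6) | 0.10 / 0.26 (3 / 8) |
| 20% | 0.13 / 0.33 (4 / 10) | 0.16 / 0.39 (5 / 12) | 0.22 / 0.55 (7 / 17) |
| 30% | 0.21 / 0.53 (6 / 16) | 0.26 / 0.64 (8 / 19) | 0.36 / 0.90 (11 / 27) |

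Simulation at A = 10.6 gave 0.06 and 0.15, 0.13 and 0.33, and 0.21 and 0.53 month, in agreement with the r = 14.1 column. At any constant accrual rate the extra subjects randomized before the looks number k/f − k: about 1 and 2 at 10%, and 3 and 7.5 at 30%.

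**Step 4: the alternative.** Suppose each toxicity stopper were counted at the date on which she would have reached 2 months. The looks would then come at 12 and 30 subjects whatever the toxicity, but with only 12f and 30f completers: 11.2 and 28.0 at 10%, 10.4 and 26.0 at 20%, 9.6 and 24.0 at 30%.

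Timing would still depend on other early stops. Appendix A says "CT or MRI radiological assessments should occur on day 1 of cycle 3", which is day 57, before two calendar months (about day 61), so a progression found at that scan can also end treatment too early to count. As an upper bound, if every progression by 2 months stopped treatment, 1 − [(1/3)(0.5^(2/4)) + (2/3)(0.5^(2/6))] = 23.5% of subjects would not count. The first look would then need 12/0.765 = 15.7 subjects with no toxicity at all.

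**The case for a change.** The strongest case for a change is the direction of the dependence. A safety review should not move later because safety is worse, these are the scheduled reviews during enrolment, and one added clause would remove the dependence on toxicity. The pooled count would need no unblinding, and reporting the number of completers would show the DRT the loss of exposure.

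The direction stands: nothing in the Synopsis counts early stoppers towards the trigger. What does not stand is that this makes the trigger defective. The supplied text attaches no fixed date, enrolment pause or stopping rule to either look, so a shift of days breaches no commitment. The additional clause also has a cost. It gives up full 2-month exposure in about a fifth of the counted subjects at a 30% stop rate, which is when such exposure tells most about tolerability. It would also make the count depend on whether a stop is recorded as an adverse event, withdrawal or investigator discretion, and would leave the other reasons for early stopping untouched.

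**Conclusion.** The concern does not hold. The literal reading of the trigger is right, but no number, rule or conclusion in the plan is wrong because of it. Early toxicity is not hidden, since the DRT "will review cumulative safety data and make recommendations regarding study conduct", without restriction to completers. The effect is on timing only: about 2 to 8 days at the first look and 5 to 19 days at the second, for assumed stop rates of 10% to 30% and the two accrual rates that fit both stated timings. The slow extreme, which misses one of those timings, reaches 11 and 27 days at 30%.

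These figures rest on assumed stop rates, constant accrual from the first day, exponential PFS with medians of 4 and 6 months, and no other early stops. Counting completers secures 12 and 30 subjects with the intended exposure; counting early stops would give a slightly earlier look with less exposure. Either is acceptable, and the choice is one of design preference.

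### Do CT/MRI scans 7 to 8 weeks apart undermine the planned Kaplan-Meier and Cox analyses of PFS?

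*Combined protocol and SAP*

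**What the plan says.** The Primary Objective in the synopsis is an estimate of the PFS hazard ratio, to guide phase 3 planning. The same paragraph describes the PFS estimates for each arm as qualitative. The Endpoints section defines PFS by modified RECIST per local review.

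Under Statistical Considerations, the median gain regarded as clinically meaningful "is 2 months (with a minimum increase of 1.5 months"), over a control median of 4 months. The smaller gain in "median PFS translates into a hazard ratio of 0.727"; the larger gives 0.667. The sample is 150 subjects, 100 against 50. The analysis at 75 events consists of "Summary statistics and Kaplan-Meier (K-M) plots of PFS by treatment arm", the Kaplan-Meier proportion event-free at 6 months, and a Cox estimate: "The stratified Cox model will be used to estimate the hazard ratio with respect to PFS", with an 80% confidence interval. The primary analysis, at about 120 events, uses the same methods.

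Appendix A, footnote i, says that CT/MRI "should occur on day 1 of cycle 3, then every 7 to 8 weeks thereafter". Footnote j adds bone scans every 11 to 12 weeks for subjects with a positive scan at screening.

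The available text (synopsis and Appendix A) gives no tie method, event-dating rule or interval-censored analysis. The full statistical section and Section 7.1.1 are not part of it, so none of these can be called missing from the plan.

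**The concern.** Progression found at a scan happened at some time since the previous one. Scans are 1.61 to 1.84 months apart and the gains of interest are 1.5 and 2 months, so the measurement grid is as coarse as the effect. Three consequences suggest themselves:

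- Kaplan-Meier medians can fall only near scan dates, and so come out late and jump between scan waves. On an exact 8-week grid, true medians of 4.0 and 5.5 months would both read week 24.
- Many events share a date. The Breslow approximation for ties pulls the Cox hazard ratio toward 1.
- An interval-censored model might recover the latent medians with less noise.

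If all this mattered, the trial would hand phase 3 a control median that is too long and a hazard ratio that is too close to 1.

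**Working it through.** **Inputs.** From Statistical Considerations: control median 4 months, test medians 6 or 5.5, 100 v 50 subjects, 120 events, 80% interval. From Appendix A, footnote i: first scan 8 weeks after day 1, then every 7 to 8 weeks. Assumed, because the available text does not give them: exponential PFS, uniform accrual over 17 months, no dropout, progression dated at the detecting scan.

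**1. The plan's own figures.** Under exponential PFS the hazard ratio is control median / test median: 4/6 = 0.667 and 4/5.5 = 0.727. Both are reproduced.

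**2. What limits separation of the two effects.**
- SE(log HR) = 1/√(120 × 2/3 × 1/3) = 0.194.
- Distance between the effects: ln(0.7273/0.6667) = 0.087, and 0.087/0.194 = 0.45 SE.
- 80% interval factor: exp(1.2816 × 0.194) = 1.28, giving 0.52 to 0.85 around 0.667 and 0.57 to 0.93 around 0.727.
- Events needed for an 80% half-width of 0.087: 4.5 × (1.2816/0.0870)² ≈ 976.

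No scan interval enters this calculation. The overlap would be the same if every progression were dated to the day.

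**3. What scan dating does to the Cox estimate.** Mean estimates from 3,000 simulated trials per setting, unstratified:

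| Event dating | True 0.667: Efron | Breslow | True 0.727: Efron | Breslow |
|---|---|---|---|---|
| Exact | 0.665 | 0.665 | 0.725 | 0.725 |
| Common 8-week grid | 0.664 | 0.698 | 0.726 | 0.756 |
| Common grid, 8 then every 7 weeks | 0.667 | 0.698 | 0.728 | 0.755 |
| Individual 7-8 week spacing | 0.667 | 0.677 | 0.726 | 0.735 |
| Same, with visit-day variation | 0.669 | 0.672 | 0.726 | 0.729 |

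The model SE is 0.192 to 0.193 in every row, and about 0.20 with four strata. Under Efron, scan dating costs the hazard ratio essentially nothing. The worst Breslow shift is ln(0.70/0.667) = 0.048, or 0.25 SE, and it needs every subject to be scanned on the same days.

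**4. Medians.** Half a scan gap is 0.80 to 0.92 month. Simulated medians run 0.74 to 0.93 month late when all events are scan-dated, and about 0.7 month late if 15% of events are exactly dated deaths. The delay is almost the same in both arms: for true medians of 6 and 4 the means are about 6.8 and 4.8, and 6.8 − 4.8 = 2.0, the true difference. A true 1.5-month difference is likewise kept at about 1.5. The SD of the difference rises from about 1.17 to 1.3-1.4 months.

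The case in which 4.0 and 5.5 months read alike depends on the grid:
- Exact 8-week scans: the medians read 5.52 and 5.52 months, a gain of 0.
- 8 then every 7 weeks: 5.06 and 6.67, a gain of 1.61.
- 8 then every 7.5 weeks: 5.29 and 7.01, a gain of 1.72.

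**5. Six-month PFS.** Six months is week 26.1, so if all events are scan-dated the curve still shows its week-24 or week-22 value. True values are 0.5^(6/4) = 0.35 and 0.5^(6/6) = 0.50. The values read are 0.38 and 0.53 at week 24, or 0.42 and 0.56 at week 22: 3 to 6 points high in each arm. The difference between arms stays at about 14 points (0.528 − 0.384 = 0.144; 0.557 − 0.416 = 0.141), against a true 0.500 − 0.354 = 0.146.

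**6. The alternative model.** A separate simulation (600 runs, 12-month accrual, 7-8 week scans, medians 6 v 4) gives these SDs for the median difference: Kaplan-Meier 1.17 on exact dates and 1.29 on scan dates; Weibull 0.90 on exact dates and 0.90 interval-censored. The gain on scan dates is 1.29 − 0.90 = 0.39. With no scan effect at all it is still 1.17 − 0.90 = 0.27, and 0.27/0.39 ≈ 70%. Most of the apparent precision therefore comes from assuming a family that contains the distribution used to generate the data.

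**The case for a change.** The best case for the concern is that phase 3 planning uses medians as well as hazard ratios. A control median of 4.8 read as true progression time is 20% too long (0.8/4), and the ratio of the scan-dated medians, 4.8/6.8 = 0.71, understates the effect. On an exact 8-week grid, a true 1.5-month gain gives an observed median difference of zero or less in 33% of simulated trials, against 5% for an interval-censored Weibull. Naming a tie method and adding a sensitivity analysis would cost little.

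The arithmetic stands; the inference does not. The plan takes its hazard ratio from the Cox model, not from a ratio of medians. The 33% belongs to a rigid grid: with scans spread over 7 to 8 weeks the figures are 8% and 5%. The 0.8 month is an error only against latent progression, whereas the endpoint is progression documented by RECIST. The documents do not say that the 4-month control median is a latent value. A phase 3 trial that also dates PFS by scan would be mistimed if it were planned on latent medians. What remains is that Kaplan-Meier medians from this trial should be read as coarse, which suits estimates the protocol itself calls qualitative, and that stating the tie method would be useful detail if the full statistical section does not already do so.

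**Conclusion.** The concern does not hold. For the primary measure, scan spacing changes neither the estimate nor its precision under Efron ties: 0.66-0.67 and 0.72-0.73 against true values of 0.667 and 0.727, with SE about 0.19. The plan cannot tell the two planning effects apart at 120 events, but it does not set out to; it names a desired and a minimum effect. An interval-censored analysis would not change that. The Breslow shift is hypothetical: about 0.03 on a rigid common grid, and about 0.01 or less with realistic spread. The delay of about 0.8 month in the medians is common to both arms and is a feature of documented progression. No decision in the available text rests on a difference in medians. Interval-censored Weibull medians would be a choice of estimand and model, not the repair of an error.

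This rests on exponential PFS, the same scan schedule in both arms, and progression dated at the detecting scan. A schedule that in practice differed between arms would need a separate look, but nothing in the available text suggests one.
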